	8.5 Analysis of Primary Endpoint(s).....	17
	8.5.1 Analysis of Primary Safety Endpoint	17
	8.5.2 Analysis of Primary Effectiveness Endpoint.....	17
	8.5.3 Criteria for Study Success	18
	8.6 Sensitivity Analyses	18
	8.6.1 Primary Safety Endpoint	18
	8.6.2 Primary Effectiveness Endpoint	19
	8.7 Subgroup Analyses	20
	8.8 Assessment of Site Homogeneity.....	21
	8.10 Handling of Missing Data	22
	8.11 Adjustments for Multiplicity	23
	8.12 Analyses of Secondary Endpoints.....	23
	8.13 Additional Endpoint Analyses	24
	8.13.1 Additional Safety Endpoints.....	24
	8.13.2 Additional Effectiveness Endpoints	24
	8.13.3 Additional Procedural Data	27
9	Data Monitoring Committee (DMC)	27
10	Reference(s).....	28

1 Study Design

This clinical investigation is an interventional, prospective, multicenter, non-randomized, single arm, premarket clinical evaluation of the Biosense Webster (BWI) Irreversible Electroporation (IRE) Ablation System (VARIPULSE™ Catheter and TRUPULSE™ Generator) to demonstrate safety and long-term effectiveness when compared to predetermined performance goals. The study will enroll subjects with drug refractory, symptomatic paroxysmal atrial fibrillation (PAF) who are candidates for catheter ablation in two sequential phases, including 1) a Pilot phase which will be used to characterize the safety profile of the BWI IRE system, and 2) a Pivotal phase which will consist of roll-in subjects to verify consistent workflow for use of the IRE system and to minimize the learning curve effect on the evaluation of safety and effectiveness of the system. The main phase subjects will be used for hypothesis testing.

For the purpose of characterization of acute safety, the Pilot phase will enroll 20 evaluable subjects from a protocol-specified maximum of 40 sites in the United States. Enrollment for the Pivotal phase will be initiated when all Pilot phase subjects have at least 30 days of follow-up, unless the Sponsor deems otherwise per section 22 (Study Suspension or Termination) of the study protocol.

The Pivotal phase of this study, roll-in and main phases combined, will enroll a maximum of 408 subjects from up to 40 sites in the United States. The Pivotal roll-in phase will enroll a maximum of 160 subjects. [REDACTED]

[REDACTED]
[REDACTED]
[REDACTED] The Pivotal main phase will enroll 248 subjects (225 evaluable subjects plus 10% attrition). Data for roll-in subjects will be analyzed separately from the main phase and will not be counted towards the enrollment cap of 225 evaluable subjects of the Pivotal main phase.

After the study ablation procedure, subjects will be followed up for 12 months, including a 3-month blanking period (Day 0-90) and followed by a 9-month evaluation period (Day 91-365). All subjects will be evaluated at 7 days, 1, 3, 6, and 12 months following the index procedure. There will be no formal interim analysis (sample size analysis or early success analysis) in this study.

2 Treatment Assignment

All subjects will be treated with the IRE Ablation System, which includes the multichannel generator (TRUPULSE™) and circular multielectrode catheter (VARIPULSE™).

3 Randomization and Blinding Procedures

This is a single-arm non-randomized trial with all subjects undergoing ablation procedure with the IRE ablation system. Therefore, masking of treatment assignment for operators and subjects is not applicable.

This study will employ several measures to minimize operational bias:

- Screening logs will be maintained at sites to confirm eligible subjects are considered for participation in the study.
- Sponsor personnel directly involved in the conduct of the study will not have access to intermediate aggregated summaries of primary safety and effectiveness endpoint data (from the Pivotal main phase) until preparation for filing for approval.

4 Interval Windows

Subjects will undergo a 3-month blanking period (Day 0-90) followed by a 9-month evaluation period (Day 91-365) and will be scheduled for evaluation at 7 days, 1, 3, 6, and 12 months following the index procedure per the table below. Discontinued subjects who had the study catheter inserted but do not undergo PFA delivery will remain in follow-up for safety for 3 months post catheter insertion and then will be discontinued from the study. All study intervals are calculated from the date of the index procedure (Day 0). Details of the pre- and post-procedure scheduled assessment are provided in the protocol.

Visit	Pre-Procedure	Ablation/Discharge		Phone/Virtual	Follow-Up Visits			
	Screening/Baseline	Study Index Procedure Day 0	Discharge	7D (D7-10)	1M (D23-37)	3M (D76-104)	6M (D150-210)	12M (D335-395)
Visit no.	1	2	3	4	5	6	7	8

5 Levels of Significance

For the Pilot phase and the Pivotal roll-in phase, no formal statistical hypothesis will be formulated or performed.

For the Pivotal main phase, the Type I error for each of the primary endpoints is controlled at a one-sided 2.5% level. The secondary endpoint will only be tested if the primary endpoints are met. The Family-wise error rate for the primary and secondary hypothesis tests will be

controlled at a level of 2.5% by using this gatekeeping strategy. All confidence intervals will utilize a two-sided 95% confidence level unless otherwise specified.

6 Analysis Sets

The analysis sets in this study are defined as the following:

6.1 Pilot Phase

- **Safety Analysis Set (SA):** [REDACTED]

6.2 Pivotal Phase

6.2.1 Pivotal Main Phase

- **Safety Analysis Set (SA):** [REDACTED]
[REDACTED]
- **Modified Intent-To-Treat (mITT) Analysis Set:** [REDACTED]
[REDACTED]
[REDACTED]
- **All Treated Analysis Set:** [REDACTED]
[REDACTED]
[REDACTED]
- **Per Protocol (PP) Analysis Set:** [REDACTED]
■ [REDACTED]
■ [REDACTED]
■ [REDACTED]
■ [REDACTED]
■ [REDACTED]

6.2.2 Pivotal Roll-In Phase

- Roll-In Analysis Set: [REDACTED]

7 Sample Size Justification

- **Pilot Phase:**
As the Pilot phase of the study is a safety characterization phase, a sample size of **20 evaluable subjects** is intended to provide preliminary estimates for safety and acute effectiveness of the IRE Ablation System.
- **Pivotal Main Phase:**

- [REDACTED]
[REDACTED]
[REDACTED]
[REDACTED]
[REDACTED]
- [REDACTED]
[REDACTED]
[REDACTED]
[REDACTED]
[REDACTED]
[REDACTED]

- **Total Sample Size:**

The sample size is mainly driven by the hypothesis test for the primary effectiveness endpoint. The sample size of **225 evaluable subjects** will provide above 80% power to declare success for each endpoint using an exact binomial test at a one-sided target alpha of 0.025.

8 Statistical Analysis Methods

For the Pilot phase and the Pivotal roll-in phase, data will be analyzed separately (not part of the primary hypothesis testing). No formal statistical hypothesis testing will be conducted, and all analyses will be descriptive. The following confidence intervals will be presented:

- Exact two-sided 95% confidence intervals for primary safety and primary and secondary effectiveness endpoints.
- Two-sided 95% confidence intervals using Greenwood's variance for Kaplan-Meier estimates for long-term effectiveness endpoints.

8.1 General Conventions

Standard descriptive summaries for continuous data include the number of observations with data, mean, standard deviation, median, 25th percentile, 75th percentile, minimum, and maximum values. For categorical data, the count and percent will be presented. Percentages will be based on the number of subjects without missing data.

10 of 10

© 2013 Pearson Education, Inc.

Digitized by [contact]

For more information, contact the Office of the Vice President for Research and the Office of the Vice President for Student Affairs.

© 2019 Pearson Education, Inc.

© 2013 Pearson Education, Inc.

© 2019 Pearson Education, Inc. All Rights Reserved. May not be copied, scanned, or duplicated, in whole or in part. Due to electronic rights, some third party content may be suppressed from the eBook and/or eChapter(s). Editorial review has determined that any suppressed content does not materially affect the overall learning experience. Pearson Education, Inc. reserves the right to remove additional content at any time if subsequent rights restrictions require it.

© 2010 Pearson Education, Inc.

■ [REDACTED]

ANSWER

Digitized by [contact]

Digitized by [contact]

For more information, contact the Office of the Vice President for Research and Economic Development at [contact] or [contact].

For more information, contact the Office of the Vice President for Research and Economic Development at [contact] or [contact].

Digitized by [contact]

For more information, contact the Office of the Vice President for Research and Economic Development at [contact] or [contact].

© 2019 Pearson Education, Inc.

1. *What is the primary purpose of the study?*

For more information, contact the Office of the Vice President for Research and Economic Development at [contact] or [contact].

8.2 Disposition of Study Subjects

Disposition and accountability of the study subjects will be summarized descriptively for the subject categories defined in section 10.6 of the study protocol.

8.3 Demographic and Baseline Characteristics

Subject demographics, medical history, previously failed AADs, active AAD use at baseline, and other baseline data will be summarized descriptively for subjects in the Pilot SA, Pivotal main study SA, mITT, and PP, and Pivotal Roll-In analysis sets.

8.4 Endpoint(s) and Associated Hypotheses

8.4.1 Primary Endpoint(s)

8.4.1.1 Primary Safety Endpoint

The primary safety endpoint is the occurrence of early onset PAEs (within 7 days of an ablation procedure which uses the VARIPULSE™ Catheter and TRUPULSE™ Generator per protocol, including initial and repeat procedures).

PAEs include the following adverse events (AEs):

Atrio-Esophageal Fistula*	Phrenic Nerve Paralysis (permanent) ⁺
Cardiac Tamponade**,***/perforation**	Pulmonary Vein Stenosis ⁺⁺
Device or procedure related death ^{†††}	Stroke/Cerebrovascular Accident (CVA) ^{†,††}
Major Vascular Access Complication/Bleeding	Thromboembolism
Myocardial Infarction	Transient Ischemic Attack (TIA)
Pericarditis	Pulmonary Edema (Respiratory Insufficiency)
Heart Block	Vagal Nerve Injury/ Gastroparesis

*Atrio-esophageal fistula occurring up to 90 days post atrial fibrillation (AF) ablation procedure will be considered a PAE.

**Cardiac Tamponade/Perforation occurring up to 30 days post AF ablation procedure will be considered a PAE.

*** Hemodynamic compromise or instability is defined as systolic blood pressure < 80 mm Hg.

[†] Absent phrenic nerve function as assessed by a sniff test. Refer to Table 14.2.1.1 in the protocol for permanent phrenic nerve paralysis definition.

⁺⁺ Pulmonary vein stenosis occurring anytime during the 12-month follow up period will be considered a PAE.

^{††} Non-focal global encephalopathy requires unequivocal evidence based upon neuroimaging studies to be reported as a stroke.

^{†††} Modified Rankin score assessments should be made by certified individuals.

^{†††} Device or procedure-related death anytime during or after the ablation procedure.

The PAE rate will be compared against a performance goal of 12% by testing the following hypothesis:

$$H_0: p_s \geq 0.12 \quad \text{vs} \quad H_A: p_s < 0.12 ,$$

Where p_s is the proportion of subjects with PAE.

8.4.1.2. Primary Effectiveness Endpoint

The primary effectiveness endpoint is freedom from documented (symptomatic and asymptomatic) atrial tachyarrhythmia (atrial fibrillation [AF], atrial tachycardia [AT], or atrial flutter [AFL] of unknown origin⁺) episodes based on electrocardiographic data (≥ 30 seconds on an electrocardiogram [ECG], sponsor-provided cardiac event monitor [CEM], or Holter device) during the effectiveness evaluation period (Day 91-365 post index procedure) and freedom from the following failure modes:

- **Acute procedural failure**, defined as failure to confirm entrance block in all pulmonary veins (except those that are silent and/or cannot be cannulated post-procedure) at the end of the procedure.
- **Repeat ablation failure**, including:
 - More than 1 repeat ablation procedures for AF/AT/AFL of unknown origin⁺ during the 3-Month Blanking Period (Day 0-90 post index procedure).
 - Any repeat ablation procedure for AF/AT/AFL of unknown origin⁺ during the evaluation period.
- **Non-study catheter failure**, including:
 - Use of a NSC to treat pulmonary vein targets to achieve isolation of clinically relevant PVs (all PVs except those that are silent and/or cannot be cannulated) and/or to ablate left atrial non-PV AF targets during the index procedure.
 - Use of a NSC to treat pulmonary vein targets to achieve isolation of clinically relevant PVs (all PVs except those that are silent and/or cannot be cannulated) during repeat procedure in the blanking period.
- **AAD failure**, defined as taking a new Class I/III AAD for atrial tachyarrhythmia (AF, AT or AFL of unknown origin⁺) or taking a previously failed Class I/III AAD at a greater than the highest ineffective historical dose for AF/AT/AFL beyond the 3-month follow-up visit window (i.e., at any time from day 105-365 post index procedure).
- **Continuous AF/AT/AFL of unknown origin⁺** on a standard 12-lead ECG during the effectiveness evaluation period.
- **Any Direct Current Cardioversion (DCCV) procedure** during the evaluation period for documented atrial tachyarrhythmia (AF, AT or AFL of unknown origin⁺) recurrences ascertained through protocol specified arrhythmia monitoring methods (12-lead ECG, CEM and Holter monitor).

⁺AFL of unknown origin is defined as all AFL except those cavotricuspid isthmus (CTI) dependent AFL as confirmed by 12-Lead ECG and entrainment maneuvers in an EP study.

The primary effectiveness endpoint will be assessed by testing the following hypothesis:

$$H_0: p_E \leq 0.50 \quad vs \quad H_A: p_E > 0.50 ,$$

Where p_E is the proportion of subjects that are free from primary effectiveness failures at 12-month follow-up.

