13.5 Post Procedure Follow-Up Assessments

The subjects will be required to complete follow up visits through 12 months (365 days) post initial ablation procedure. Follow-up schedules will be based on a 30-day month.

Follow-up visits should be scheduled according to the following timeframes: 7 day +3 days (7D, day 7-10), 1 month \pm 7 days (1M, day 23-37), 3 month -14 days (3M, day 76-104), 6 months \pm 30 days (6M, day 150-210), and 12 month \pm 30 days (12M, day 335-395). Follow-up visit schedule will not reset if subject undergoes a repeat AF ablation procedure.

The following should be performed prior to hospital discharge:

- Physical exam including standardized neurological examination: Exam should be performed by a physician or equivalent (NP or PA). The following items will be evaluated as part of the standardized neurological examination: mental status (e.g. orientation, attention, vision, hearing, speech, level of consciousness), cranial nerve testing, assessment of gait and coordination, ability to move all extremities, and evaluation of sensory and motor strength of all 4 extremities.
- MUST be performed pre-discharge.
 - If physical exam demonstrates new abnormal neurological findings as compared to the one performed at baseline, a formal neurological consult and examination with appropriate imaging (i.e., DW-MRI) needs to be done to confirm or rule out any suspected diagnosis of stroke.
 - Diagnosis of stroke/CVA must be confirmed by at least one of the following:
 - Neurology or neurosurgical specialist
 - Neuroimaging procedure (MR or CT scan or cerebral angiography)
 - Lumbar puncture (i.e., spinal fluid analysis diagnostic of intracranial hemorrhage)
 - Stroke: (diagnosis as above, preferably with positive neuroimaging study)
 - Minor—Modified Rankin score <2 at 30 and 90 days
 - Major—Modified Rankin score \geq 2 at 30 and 90 days
 - MRS assessments should be made by certified individuals
- AFL/AT/AF recurrence
- Electrocardiogram (12-Lead ECG)
- Transthoracic Echocardiogram (TTE), for evaluation pericardium for possible pericardial effusion and/or pericarditis. In the event significant pericardial effusion is identified, subjects should be followed until the condition resolves.

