- Cardiac-related concomitant medications (such as AADs, anticoagulation regimen, etc.) All cardiac-related medications prescribed since the ablation procedure till the end of follow-up will be recorded, including the type and name of the medication, associated indications, starting and ending dates of the prescriptions, etc.
- Documentation of Adverse events (if any).

Data collected at the 7 day, 1M, 3M, 6M, and 12M follow-up, and at any unscheduled visits:

- Physical Exam including standardized neurological examination: Exam should be performed by a physician or equivalent (NP or PA). The following items will be evaluated as part of the standardized neurological examination: mental status (e.g. orientation, attention, vision, hearing, speech, level of consciousness), cranial nerve testing, assessment of gait and

coordination, ability to move all extremities, and evaluation of sensory and motor strength of all 4 extremities.. Exam should be performed at all clinical visits.

- Quality of Life questionnaire: AFEQT™ CCS-SAF are to be collected at the 3M, 6M, and 12M visits.
- Electrocardiogram (12-Lead ECG). Data from 12-lead ECG recordings will be collected at the 3M, 6M and 12M follow-up visits. ECG data will be collected at unscheduled visits if completed as standard of care.
- Transtelephonic Monitoring (TTM): TTMs will be provided to each subject no later than at the 1M visit. Subjects will be asked to transmit any symptom-triggered episode that occurs from the time they receive the TTM device through the 12M follow-up visit. Refer to Schedule of Treatments and Evaluations for required transmission schedule. Transmissions should be recorded for a minimum of 60 seconds. A core lab will be used to evaluate and assess the TTM tracings.
- 24 Hour Holter: Holter monitor will be used at the 6M and 12M follow-up visits to monitor the subjects' heart rhythm for 24 hours continuously. A core lab will be utilized to evaluate and assess the 24-hour Holter recordings.
- Cardiac Multi Slice CT/MRA Image: Any subjects who have symptoms suggestive of PV stenosis should undergo CT/MRA imaging.
- Adverse Events: AEs must be collected from the time the subject signs the informed consent onwards.
- AFL/AT/AF recurrence
 - For subjects with AFL recurrence identified through TTM and/or Holter monitoring, a 12 Lead ECG MUST be collected.

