13.8 Heart Rhythm Monitoring

ECG, TTM and Holter Monitors will be used to monitor the subjects' heart rhythm post-treatment.

TTMs:

TTMs will be provided to each subject no later than at the 1-month follow-up visit for scheduled transmissions of heart rhythm status. Subjects will be instructed to transmit following a detailed schedule beginning from their 1-month follow-up visit and during any emergent symptomatic cardiac episodes.

The TTM transmission schedule:

- Subjects will complete a test transmission upon receipt of the TTM device to demonstrate a working understanding of the device.
- Transmissions should be performed once every week starting when the subject receives their TTM (no later than at the 1-month follow-up visit) through the end of month 5 post-procedure (Weekly transmissions are required starting from the evaluation period, 91 days post-procedure through the end of month 5 post-procedure.
- Starting from month 6 post-procedure, subjects MUST record and transmit once every month until the end of the evaluation period, 365 days post-procedure.
- TTM transmission period:
 - Weekly transmissions: 7-day period
 - Monthly transmissions: 30-day period starting after the last weekly TTM window at the end of month 5 post-procedure
- In addition, all emergent symptomatic cardiac episodes from the time the TTM device is dispensed should be recorded and, promptly, transmitted.

Holter Monitors:

Subjects will be provided with a Holter monitor and instructions for the 24-hour recording, no later than at the 6-month follow-up visit. 24-hour recordings will be obtained at the 6-month and 12-month time periods.

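### Does a 12-month visit window that runs to Day 395 undermine a primary endpoint that closes at Day 365?

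*SAP*

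**What the plan says.** SAP 8.4.1.2 limits the arrhythmia component to episodes recorded "during the effectiveness evaluation period (Day 91-365 post index procedure) and freedom from the following failure modes". Continuous arrhythmia on a 12-lead ECG is a failure mode in the same period. The hypothesis in that section concerns "the proportion of subjects that are free from primary effectiveness failures at 12-month follow-up".

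Protocol 13.5 asks subjects to "complete follow up visits through 12 months (365 days) post initial ablation procedure", but sets the last visit window as "12M, day 335-395"; the table in SAP 4 gives the same window. On recordings, Protocol 13.5 says "Holter monitor will be used at the 6M and 12M follow-up visits" and "Data from 12-lead ECG recordings will be collected at the 3M, 6M and 12M follow-up visits". Protocol 13.8 is looser on the Holter: "24-hour recordings will be obtained at the 6-month and 12-month time periods". Scheduled transtelephonic transmissions are weekly through month 5, then monthly until Day 365. Of each one the Protocol says "Transmissions should be recorded for a minimum of 60 seconds".

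SAP 8.5.2 tests the success proportion in the per-protocol set, among subjects with a non-missing outcome, by an exact binomial test against 50% at one-sided 2.5%. The per-protocol definition (SAP 6.2.1), part of 8.5.2, the content of the 8.6.2 sensitivity analyses and the effectiveness bullet of 8.10 are redacted.

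**The concern.** Almost half of the permitted days for the 12-month visit fall after the endpoint has closed. The Holter at that visit is one of only two, so 24 of 48 scheduled Holter hours can fall outside the counted period without any protocol deviation. From the 6-month visit to Day 365, the remaining scheduled recording is a short monthly transmission.

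The trial has one arm and a fixed goal, so no control group shares a loss of detection. If subjects with late recordings are scored as successes, any in-window arrhythmia that a timely Holter would have caught is missed, and that error can only raise the success rate. If they are scored as missing, the analysed number falls instead. The hypothesis statement refers to 12-month follow-up without a day limit, and SAP 4 lets the 12-month visit run to Day 395, so one could also argue that a late positive recording should count. At stake is the classification of some subjects in the primary test.

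**Working it through.** **1. Visit window.** Days 335 to 395 are 395 − 335 + 1 = 61 days. Days 366 to 395 are 30 days. Share after closure: 30/61 = 49.2%.

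**2. Which reading the text supports.**

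| Place | Bearing on a Day 366-395 recording |
|---|---|
| SAP 8.4.1.2, definition | Day 91-365 is explicit: does not count |
| SAP 8.4.1.2, hypothesis | Tests freedom from primary effectiveness failures, which the same section has just bounded at Day 365: does not count |
| SAP 1 and 4; Protocol Synopsis and Section 9 (primary effectiveness endpoint) | Evaluation period ends at Day 365: does not count |
| Protocol 13.8 | Evaluation period ends 365 days after the procedure: does not count |
| Protocol 13.5 | Equates 12 months with 365 days, but allows the visit to Day 395: sets when subjects may attend, not what counts |

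The by-date reading is clear. What the visible text does not say is whether a subject whose 12-month ECG and Holter both fall late has a non-missing outcome.

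**3. Success threshold.** The plan's stated power (above 80%) cannot be reproduced because the assumed rate is redacted, but the decision rule can be derived. It is the smallest count whose exact two-sided 95% lower bound exceeds 0.50.

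- n = 225: 127 gives 0.4969 (fails); 128 gives 0.5014 (succeeds). 128/225 = 56.9%.
- n = 200: 114 gives 0.4983 (fails); 115 gives 0.5033 (succeeds). 115/200 = 57.5%.

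At n = 225, power reaches 80% at a true rate of 59.4% and is 84.6% at 60%.

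**4. If late subjects are scored as successes.** Let f be the share of 12-month recordings made after Day 365, and q the share of subjects whose only failure would be on the 12-month ECG or Holter, taken as equal in early and late attenders. Neither is in the documents; both ranges are assumptions. Difference in success rate = f × q.

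| f | q | f × q | × 225 subjects |
|---|---|---|---|
| 0.10 | 0.01 | 0.10 points | 0.2 |
| 0.25 | 0.03 | 0.75 points | 1.7 |
| 0.492 | 0.05 | 2.46 points | 5.5 |

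The last row needs visits spread evenly over the window and every Holter tied to its visit.

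**5. Successes that must be lost to reverse a positive result** (observed count − 127): 128 → 1; 133 → 6; 135 (60%) → 8. So the extreme row, rounded up to 6, matters only for 128 to 133 observed successes (56.9% to 59.1%).

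**6. If late subjects are scored as missing.** This costs precision. If all subjects with late recordings are dropped:

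| Late share (assumed) | Analysed | True rate needed for 80% power |
|---|---|---|
| 0% | 225 | 59.4% |
| 10% | 202 | 60.1% |
| 25% | 169 | 60.8% |
| 49% | 115 | 63.3% |

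**7. Other detection before Day 365.** With 30-day months, and if the last weekly transmission window ends on Day 150, the full monthly windows that start after the 6-month visit and end by Day 365 number 7 (visit on Day 150), 6 (Day 180) or 5 (Day 210). Symptom-triggered transmissions and unscheduled ECGs come on top.

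**The case for a change.** The best case for acting is that a classification which feeds the primary test should be written down before data are seen, and that a sentence costs almost nothing. The plan does align the endpoint with a visit window at 3 months: the antiarrhythmic-drug failure clock starts on Day 105, the day after that visit window closes. No matching alignment is visible at 12 months. The effect is not negligible everywhere either. At a 60% success rate, a drop of 0.5 points takes power from 84.6% to 80.7%, and a drop of 2.5 points takes it to 60.1%.

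The mismatch and these figures stand. The call for a change does not. The open question concerns missing data, and the SAP has an effectiveness entry under that heading whose content cannot be read; its absence cannot be claimed. The SAP also names worst-case, tipping-point and Kaplan-Meier analyses, which may already cover such subjects.

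A further sensitivity run counting positive ECGs and Holters from Day 366-395 would not measure the loss at issue. It adds events from outside the endpoint and makes the period at risk depend on attendance: up to 305 days (Day 91-395) against 275 (Day 91-365). Unless it also admitted late symptom-triggered transmissions, repeat ablations, cardioversions and drug failures, it would be a hybrid of two endpoints. Adding a day limit to the hypothesis sentence would alter no result.

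**Conclusion.** No change to the plan follows. A visit window that extends past an endpoint date is a common trade-off between feasible attendance and a fixed horizon, and here the horizon is stated consistently. Under it, leaving out an arrhythmia first recorded on, say, Day 380 is correct classification; the only possible loss is a 12-month recording that was not made in time.

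If those subjects are scored as successes, the loss is about 0.75 points (1.7 subjects) at 25% late and 3% yield, and 2.5 points (5.5 subjects) at the extreme. It could alter the conclusion only for a result close to 128/225. If they are scored as missing, power falls as the late share rises. Both statements rest on assumed late shares, and the first also on assumed yields, with 225 subjects as the starting number.

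The remaining question, complete or missing, is one that analysts can settle under the missing-data section, and the redacted text may already settle it. Confidence is moderate because of the redaction.
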